8.6 Accountability and Destruction of All Study Medication

Drug supplies will be counted and reconciled at the site before being returned to Takeda or designee or being destroyed.

The investigator or designee must ensure that the study medication is used in accordance with the approved protocol and is dispensed only to subjects enrolled in the study. To document appropriate use of study medication (TAK-491 or placebo) the investigator must maintain records of all study medication delivery to the site, site inventory, use by each subject, and return to the sponsor or designee.

Upon receipt of study medication, the investigator or designee must verify the contents of the shipments against the packing list. The verifier should ensure that the quantity is correct, the medication is received within the labeled storage conditions, and is in good condition. If quantity and conditions are acceptable, investigator or designee should acknowledge the receipt of the shipment. If there are any discrepancies between the packing list versus the actual product received, Takeda must be contacted to resolve the issue. The packing list should be filed in the investigator's essential document file.

The investigator must maintain 100% accountability for all study medication received and dispensed during his or her entire participation in the study. Proper drug accountability includes, but is not limited to:

- Continuously monitoring expiration dates if expiration date is provided to the investigator.
- Frequently verifying that actual inventory matches documented inventory.
- Verifying that the log is completed for the drug lot used to prepare each dose.
- Verifying that all containers used are documented accurately on the log.
- Verifying that required fields are completed accurately and legibly.

If any dispensing errors or discrepancies are discovered, the sponsor must be notified immediately.

The investigator must record the current inventory of all study medication (TAK-491 or placebo) on a sponsor-approved drug accountability log. The following information will be recorded at a minimum: protocol number and title, name of investigator, site identifier and number, description of study medication, expiry and/or retest date, date and amount dispensed, including the initials of the person dispensing and receiving the study medication. The log should include all required information as a separate entry for each subject to whom study medication is dispensed.

Prior to site closure or at appropriate intervals, a representative from the sponsor or its designee will perform clinical study material accountability and reconciliation before clinical study materials are returned to the sponsor or its designee for destruction or destroyed at the site, as applicable. The investigator will retain the original documentation regarding clinical study material accountability, return, and/or destruction, and copies will be sent to the sponsor or designee.

The investigator will be notified of any expiry date or retest date extension of clinical study material during the study conduct. On expiry date notification from the sponsor or designee, the site must complete all instructions outlined in the notification, including segregation of expired clinical study material for return to the sponsor or its designee for destruction.

In the event of expiry date extension of supplies already at the study site, supplies may be relabeled with the new expiry date at that site. In such cases, Takeda or its designee will prepare additional labels and all necessary documentation for completion of the procedure at the sites.

9.0 STUDY PLAN

9.1 Study Procedures

The following sections describe the study procedures and data to be collected. For each procedure, subjects are to be assessed by the same investigator or site personnel whenever possible. The Schedule of Study Procedures is located in [Appendix A](#).

9.1.1 Informed Consent Procedure

The requirements of the informed consent are described in Section [15.2](#).

Informed consent must be obtained prior to the subject entering into the study, and before any protocol-directed procedures are performed.

A unique subject identification number (subject number) will be assigned to each subject at the time that informed consent is obtained; this subject number will be used throughout the study.

9.1.2 Demographics, Medical History, and Medication History Procedure

Demographic information to be obtained will include date of birth, sex, race as described by the subject, and smoking status of the subject at Screening.

Medical history to be obtained will include determining whether the subject has any significant conditions or diseases relevant to the condition/disease under study that stopped at or prior to informed consent. Ongoing conditions are considered concurrent medical conditions (see Section [9.1.7](#)).

Medication history information to be obtained includes any medication relevant to eligibility criteria stopped at or within 28 days prior to signing of informed consent.

9.1.3 Physical Examination Procedure

A physical examination will consist of the following body systems: (1) eyes; (2) ears, nose, throat; (3) cardiovascular system; (4) respiratory system; (5) gastrointestinal system; (6) dermatologic system; (7) extremities; (8) musculoskeletal system; (9) nervous system; (10) lymph nodes; and (11) other.

Any abnormal finding on a pretreatment physical examination assessment must be assessed as Not Clinically Significant (NCS) or Clinically Significant (CS) by the investigator and recorded in the source document and CRF. All CS findings/changes will be recorded as a PTE or concurrent medical condition in the source document and on the appropriate CRF described in Section [9.1.7](#) or Section [10.0](#).

On subsequent examinations, any abnormal change from the pretreatment physical examination assessment occurring immediately prior to the start of the investigational drug (Day 1) must be assessed as NCS or CS by the investigator and recorded in the source document and CRF. Any CS change, as determined by the investigator, will be recorded as an AE in source documentation and on the PTE/AE CRF described in Section [10.0](#).

9.1.4 Weight, Height, and BMI

A subject should have weight and height measured while wearing indoor clothing and with shoes off. The BMI is calculated using metric units with the formula provided below:

$$\text{Metric: } \text{BMI} = \text{weight (kg)}/\text{height (m)}^2$$

Height will be collected in centimeters without decimal places and weight will be collected in kilograms to 1 decimal place. Results for BMI will be expressed with 1 decimal place.

Example:

Height=176 cm (or 1.76 m), weight=79.2 kg; $\text{BMI}=79.2/1.76^2=25.6 \text{ kg/m}^2$.

9.1.5 Vital Sign Procedure

Vital signs will include body temperature (oral) measurement, sitting blood pressure (after 5 minutes resting), respiration rate and pulse (bpm).

When vital signs are scheduled at the same time as blood draws, the blood draw will take priority and vital signs will be obtained within 0.5 hour before or after the scheduled blood draw.

9.1.6 Documentation of Concomitant Medications

Concomitant medication is any drug given in addition to the study medication. These may be prescribed by a physician or obtained by the subject over the counter. Concomitant medication is not provided by Takeda. At each study visit, subjects will be asked whether they have taken any medication other than the study medication (used from signing of informed consent through the end of the study), and all medication, including vitamin supplements, over-the-counter medications, and oral herbal preparations, must be recorded in the CRF. Documentation will include generic medication name, dose, unit, frequency, route of administration, start and end dates, and reason for use.

9.1.7 Documentation of Concurrent Medical Conditions

Concurrent medical conditions are those significant ongoing conditions or diseases that are present at signing of informed consent. This includes clinically significant laboratory, electrocardiogram (ECG), or physical examination abnormalities noted at the Screening examination. The condition (ie, diagnosis) should be described.

9.1.8 Procedures for Clinical Laboratory Samples

All samples will be collected in accordance with acceptable laboratory procedures. The approximate total volume of blood for the study is 243 mL. Laboratory samples will be taken following a minimum 8-hour overnight fast on the days stipulated in the Schedule of Study Procedures ([Appendix A](#)).

[Table 9.a](#) lists the tests that will be obtained for each laboratory specimen.

Table 9.a Clinical Laboratory Tests

Hematology	Serum Chemistry	Urinalysis
Red blood cells	Alanine aminotransferase	pH
White blood cells with differential (neutrophils, eosinophils, basophils, lymphocytes, monocytes)	Albumin	Specific gravity
Hemoglobin	Alkaline phosphatase	Protein
Hematocrit	Aspartate aminotransferase	Glucose
Platelets	Total bilirubin	Blood
	Total protein	Ketones
	Creatinine	Microscopic Analysis (a):
	Blood urea nitrogen	RBC/high power field WBC/high
	Creatine kinase	power field
	γ -Glutamyl transferase	Epithelial cells, casts etc.
	Potassium	
	Sodium	
	Glucose	
	Chloride	
	Triglycerides	
	HDL-C	
	LDL-C	
	Total cholesterol	

Diagnostic Screening:

Serum	Urine	Breath
HBsAg, anti-HCV, anti-HIV (b)	Drug screen, including amphetamines, barbiturates, benzodiazepines, cannabinoids, cocaine, opiates, and cotinine	Breath alcohol test
Additional Virology Tests:		
Anti-HBsAb, HBeAg, anti-HBeAb, anti-HBcAb, EBV VCA IgG, EBV VCA IgM, Anti-CMV IgG, and Anti-CMV IgM (c)		

Female Subjects only:

Serum hCG at Screening, Check-in, and Study Exit or Early Termination

EBV= Epstein-Barr virus viral capsid antigen, hCG=human chorionic gonadotropin, RBC=red blood cell, WBC=white blood cell.

(a) Microscopic analysis should be performed only if urine evaluations are abnormal.

(b) HBsAg, anti-HCV, and anti-HIV test results will be collected for all subjects.

(c) The results for the additional virology tests performed at Screening will be recorded in the (e)CRF for randomized subjects only.

The local laboratory will perform laboratory tests for hematology, serum chemistries, and urinalysis. The results of laboratory tests will be returned to the investigator, who is responsible for reviewing and filing these results.

If subjects experience ALT or AST $>3 \times$ ULN, follow-up laboratory tests (at a minimum, serum alkaline phosphatase, ALT, AST, total bilirubin, GGT, and INR) should be performed within a maximum of 7 days and preferably within 48 to 72 hours after the abnormality was found. (Please refer to Section 7.5 for discontinuation criteria, and Section 10.2.3 for the appropriate guidance on Reporting of Abnormal Liver Function Tests in relation to ALT or AST $>3 \times$ ULN in conjunction with total bilirubin $>2 \times$ ULN.)

If the ALT or AST remains elevated $>3 \times \text{ULN}$ on these 2 consecutive occasions, the investigator must contact the Medical Monitor for consideration of additional testing, close monitoring, possible discontinuation of study medication, discussion of the relevant subject details and possible alternative etiologies.

Subjects with ALT/AST elevations $>1 \times \text{ULN}$ on Day 11 and/or 14 will be followed-up every 5 to 7 days until resolution.

All laboratory safety data will be transferred electronically to Takeda or designee in the format requested by Takeda. If the laboratory is unable to electronically transfer data, the study site coordinator or designee is responsible for transcribing laboratory results to the CRF. The investigator will maintain a copy of the laboratory accreditation and the reference ranges for the laboratory used.

Laboratory reports must be signed and dated by the principal investigator or subinvestigator indicating that the report has been reviewed and any abnormalities have been assessed for clinical significance.

All clinically significant laboratory abnormalities must be recorded as a PTE/AE in the subject's source documents and on the appropriate CRF. A clinically significant laboratory abnormality that has been verified by retesting will be followed until the abnormality returns to an acceptable level or a satisfactory explanation has been obtained. Please refer to Section 10.2.3 Reporting of Abnormal Liver Function Tests for reporting requirements.

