7.5 Criteria for Discontinuation or Withdrawal of a Subject

The primary reason for discontinuation or withdrawal of the subject from the study should be recorded in the case report form (CRF) using the following categories. For screen failure subjects, refer to Section 9.1.14.

1. Pretreatment event (PTE) or adverse event (AE). The subject has experienced a PTE or AE that requires early termination because continued participation imposes an unacceptable risk to the subject's health or the subject is unwilling to continue because of the PTE or AE.
 - Liver Function Test Abnormalities
 - ALT or AST $>8 \times$ ULN, or
 - ALT or AST $>5 \times$ ULN and persists for more than 2 weeks, or
 - ALT or AST $>3 \times$ ULN in conjunction with elevated total bilirubin $>2 \times$ ULN or international normalized ratio (INR) >1.5 , or ALT or AST $>3 \times$ ULN with appearance of fatigue, nausea, vomiting, right upper quadrant pain or tenderness, fever, rash and/or eosinophilia ($>5\%$).
2. Significant protocol deviation. The discovery after administration of the first dose of study medication that the subject failed to meet protocol entry criteria or did not adhere to protocol requirements, and continued participation poses an unacceptable risk to the subject's health.
3. Lost to follow-up. The subject did not return to the clinic and attempts to contact the subject were unsuccessful. Attempts to contact the subject must be documented.

4. Voluntary withdrawal. The subject (or subject's legally acceptable representative) wishes to withdraw from the study. The reason for withdrawal, if provided, should be recorded in the CRF.

Note: All attempts should be made to determine the underlying reason for the withdrawal and, where possible, the primary underlying reason should be recorded (ie, withdrawal due to an AE should not be recorded in the "voluntary withdrawal" category).

5. Study termination. The sponsor, IRB, IEC, or regulatory agency terminates the study.

6. Pregnancy. The subject is found to be pregnant.

Note: If the subject is found to be pregnant, the subject must be withdrawn immediately. The procedure is described in Section [9.1.10](#).

7. Other.

Note: The specific reasons should be recorded in the "specify" field of the CRF.

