9.4 Blood Volume

Total blood sampling volume for an individual subject is shown in [Table 9.d](#).

Table 9.d Approximate Blood Volume

Sample Type	Sample Volume (mL)	Number of Samples			Total Volume (mL)
		Screening	Single Dose	Multiple Dose with Study Exit	
Safety Laboratory Samples	15	2	1	2	75
Pharmacokinetic Samples	6	N/A	14	17	186
Total Blood Sampling Volume					261

Direct venipuncture is the method of blood collection. Additional blood samples may be collected at the discretion of the investigator to assess safety.

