11.0 STUDY-SPECIFIC COMMITTEES

No steering committee or clinical endpoint committee will be used in this study.

Takeda will designate an external hepatologist as an independent assessor of any liver enzyme elevation in the study. Takeda will also designate a Pharmacovigilance physician who is not involved in the study conduct as a sponsor liaison to participate and facilitate the safety communication between the external expert, the study site and Takeda.

All liver enzyme elevations occurring in the study subjects will be initially submitted to blinded review by the external hepatologist. The unblinded aggregate data from a series of patients will also be reviewed by the external hepatologist, a designated independent physician from the site, and a sponsor liaison before the next cohort is dosed with the support of an independent statistician, and a written assessment will be provided to Takeda liaison and the study PI in a real time.

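### Protocol 9.1.8 lets the first INR after a Day 4 ALT/AST above 3×ULN wait until Day 11 or 12, after the last dose on Day 10, so an INR stopping criterion may go unmeasured while doses remain.

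*Protocol*

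**What the plan says.** Study drug is given on Days 1 and 4 to 10 (Protocol 8.1.3). Between the first and last dose there is one scheduled safety panel, before dosing on Day 4 (Appendix A, footnote h). Sections 9.3.6 and 9.3.7 list no clinical laboratory tests for Days 5 to 10, and the next panel is on Day 11. Table 9.a includes ALT, AST, total bilirubin and a white-cell differential, but not INR.

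Section 7.5 gives three routes to a liver-test stop:

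- ALT or AST above 8×ULN.
- ALT or AST above 5×"ULN and persists for more than 2 weeks".
- ALT or AST above 3×ULN with any one of: total bilirubin above 2×ULN, "international normalized ratio (INR) >1.5", or a listed clinical feature. The listed features are fatigue, nausea, vomiting, "right upper quadrant pain or tenderness, fever, rash and/or eosinophilia" (above 5%).

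For ALT or AST above 3×ULN, Section 9.1.8 asks for "follow-up laboratory tests (at a minimum, serum alkaline phosphatase, ALT, AST, total bilirubin, GGT, and INR"). On timing it reads "total bilirubin, GGT, and INR) should be performed within a maximum of 7 days and preferably within 48 to 72 hours", counted from when the abnormality was found. If the repeat is also above 3×ULN, "the investigator must contact the Medical Monitor for consideration of additional testing, close monitoring, possible discontinuation of study medication".

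Section 11.0 adds that "All liver enzyme elevations occurring in the study subjects will be initially submitted to blinded review by the external hepatologist". Section 9.4 adds that "Additional blood samples may be collected at the discretion of the investigator to assess safety".

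**The concern.** A stopping rule protects a subject only if its components are measured while there is still a dose to withhold. Here one laboratory component, INR, is required only in a repeat panel whose outer limit runs past the end of dosing. Repeat ALT, AST and bilirubin can wait equally long. Eosinophils are known from Day 4 but need not be measured again before Day 11, because the minimum repeat panel has no differential. Section 9.1.8 does not hold drug pending the repeat, and mandatory contact with the Medical Monitor depends on the repeat, so a late repeat delays that step too.

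This matters more than usual in this study. Section 6.2 reports that 15 of the first 16 subjects had higher ALT and/or AST on Day 11 than on Day -1, and that 7 exceeded the ULN. The double-blind, placebo-controlled part was added because a drug effect had to be ruled out. Section 6.2 also names diet and low activity during confinement as possible causes, and says the rises resolved without intervention. The cause was therefore open, not established.

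**Working it through.** The plan gives no figure to reproduce beyond the 7-day limit itself. The check is study-day arithmetic.

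**Inputs**

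- Dose days: {1, 4, 5, 6, 7, 8, 9, 10}, 8 doses (8.1.3).
- Triggering sample: Day 4, predose (Appendix A, footnote h).
- Day found: Day 4, or Day 5 if the result is read the next day. The documents give no laboratory turnaround time, so Day 5 is an assumption.
- Limit for the repeat: 7 days, with 48 to 72 hours preferred (9.1.8).
- Entry cap: ALT and AST at or below 1.5×ULN at Screening and Day -1 (7.2, No. 17).

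**Step 1: which 7.5 routes can act by Day 10 for a subject above 3 and up to 8×ULN?**

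- The 8×ULN route does not apply, by definition.
- The 5×ULN route needs more than 14 days. From the Day 4 sample, 4 + 14 = Day 18, so it is first met on Day 19. The entry cap means the rise cannot predate Day -1. With no Day 0 (SAP 7.1.3), Day -1 plus 14 days is Day 14. Both dates are after Day 10.
- Only the combination route is left. Day 4 supplies bilirubin and eosinophils, and AEs are assessed daily. INR is not available.

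**Step 2: latest compliant day for the first INR.** Day found + 7:

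- Found Day 4: 4 + 7 = Day 11.
- Found Day 5: 5 + 7 = Day 12.

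Both are after the last dose. Required INR or eosinophil measurements after the Day 4 sample and before the last dose: 0.

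**Step 3: doses that can still be withheld.** For a repeat drawn predose on day d, count dose days ≥ d if the result is known before that day's dose, or > d if it is known afterwards.

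| Finding | Limit | Repeat day d | Result before dose on d | Result after dose on d |
|---|---|---|---|---|
| Day 4, after dosing | 7 days | 11 | 0 | 0 |
| Day 5 | 7 days | 12 | 0 | 0 |
| Day 4, after dosing | 72 hours | 7 | {7, 8, 9, 10} = 4 | {8, 9, 10} = 3 |
| Day 5 | 72 hours | 8 | {8, 9, 10} = 3 | {9, 10} = 2 |

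**The case against.** The strongest reply is that the protocol already states the right interval. Forty-eight to 72 hours is the stated preference, subjects are confined through Day 11, and nothing in the documents stands in the way of meeting it. A site that follows the preference repeats the panel on Days 6 to 8, and the proposed change gains nothing over that. This is true. But the preference does not bind, and the 7-day limit from Day 4 coincides with the Day 11 exit panel, which makes waiting convenient.

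Second, the case needs several conditions at once: a rise from at most 1.5×ULN to above 3×ULN by Day 4, no symptoms, bilirubin and eosinophils below the limits, and no use of discretionary samples or of the general unacceptable-risk criterion in 7.5. For a stop actually to be missed, INR must also exceed 1.5. This stands, and it limits the weight of the point. The open-label result (0 of 16 above 3×ULN) also points to rarity, but it was observed on Day 11 and does not estimate the Day 4 rate.

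Third, Section 11.0 asks for a written assessment in real time. That phrase is in the sentence on unblinded aggregate review before the next cohort. Even if read as covering single cases, it requires neither a retest nor an INR by any date.

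Fourth, a 72-hour limit still allows the doses of Days 4 to 6 (Days 4 to 7 if found on Day 5) before any INR is known. This is correct. The change makes the stopping criterion usable in time; it does not make it immediate.

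**Conclusion.** The concern holds. For a symptom-free subject with Day 4 ALT or AST above 3 and up to 8×ULN, and Day 4 bilirubin and eosinophils below the 7.5 limits, a fully compliant site may first measure INR on Day 11 or 12, with 0 doses left to withhold. A binding 72-hour limit leaves 2 to 4.

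The Day 12 figure, and the lower end of that range, assume that the Day 4 result is read on Day 5. The gap is narrow: a value above 8×ULN, a Day 4 bilirubin or eosinophil result over the limit, a listed symptom on any day, or the investigator's judgement can still stop dosing. Frequency cannot be estimated from the documents and is probably low. The change should be made because it costs little and lets a stated stopping criterion operate in time. The 7.5 thresholds are not in question.

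**What to change.** In Section 9.1.8, for any ALT or AST above 3×ULN found while doses remain:

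- Require the repeat panel no later than 72 hours after the finding, including INR and adding hematology with differential.
- Draw it before that day's dose, and review the results against Section 7.5 as soon as they are available.
- Keep the 7-day limit for findings on Day 11 or Day 14.
- State that a stop already met on the Day 4 sample is not delayed by the repeat.

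This adds no mandatory hold; dosing before the repeat stays at the investigator's judgement.

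The cost is one or two lines of text, with the ethics approval that any protocol change needs. Affected subjects have one extra hematology tube, and an INR that is already required is done sooner. No visit is added, because subjects are confined through Day 11. A predose repeat on Day 7 or 8 can be drawn with the trough PK sample already scheduled on Days 7 to 9.
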